4.5.4.1 Severe skin reactions

Immune-mediated severe skin reactions have been reported in patients treated with pembrolizumab. Monitor patients for suspected severe skin reactions and exclude other causes. Based on the severity of the adverse reaction, withhold or permanently discontinue pembrolizumab and administer corticosteroids

Cases of Stevens-Johnson syndrome (SJS) and toxic epidermal necrolysis (TEN), some with fatal outcome, have been reported in patients treated with pembrolizumab. For signs or symptoms of SJS or TEN, withhold pembrolizumab and refer the patient for specialized care for assessment and treatment. If SJS or TEN is confirmed, permanently discontinue pembrolizumab.

4.5.4.2 Other Immune-Mediated Adverse Reactions

The following additional clinically significant, immune-mediated adverse reactions were reported in less than 1% of patients treated with pembrolizumab in KEYNOTE-001, KEYNOTE-002, KEYNOTE-006, and KEYNOTE-010: uveitis, myositis, Guillain-Barré syndrome, and pancreatitis. The following was reported in other clinical studies with pembrolizumab or in post-marketing use: myocarditis.

Cases of these immune-mediated adverse reactions, some of which were severe, have been reported in clinical trials or in post-marketing use.

Solid organ transplant rejection has been reported in the post-marketing setting in patients treated with pembrolizumab. Treatment with pembrolizumab may increase the risk of rejection in solid organ transplant recipients. Consider the benefit of treatment with pembrolizumab versus the risk of possible organ rejection in these patients.

4.6 Concomitant Medications/Treatments

Medications or vaccinations specifically prohibited in the exclusion criteria are not allowed during the ongoing trial. If there is a clinical indication for one of these or other medications or vaccinations specifically prohibited during the trial, discontinuation from trial therapy or vaccination may be required. The investigator should discuss any questions regarding this with the Sponsor. The final decision on any supportive therapy or vaccination rests with the investigator and/or the subject's primary physician. However, the decision to continue the subject on trial therapy or vaccination schedule requires the mutual agreement of the Investigator, the Sponsor, and the subject.

4.6.1 Acceptable Concomitant Medications

All treatments that the investigator considers necessary for a subject's welfare may be administered at the discretion of the investigator in keeping with the community standards of medical care. All concomitant medication will be recorded on the case report form (CRF) including all prescription, over-the-counter (OTC), herbal supplements, and IV medications and fluids. If changes occur during the trial period, documentation of drug dosage, frequency, route, and date may also be included on the CRF.

All concomitant medications received within 28 days before the first dose of trial treatment and 30 days after the last dose of trial treatment should be recorded. Concomitant medications administered after 30 days after the last dose of trial treatment should be recorded for SAEs.

4.6.2 Prohibited Concomitant Medications

Subjects are prohibited from receiving the following therapies during the Screening and Treatment Phase of this trial:

- Anti-cancer systemic chemotherapy or biological therapy
- Anti-cancer immunotherapy not specified in this protocol
- Chemotherapy not specified in this protocol
- Investigational agents other than pembrolizumab
- Radiation therapy
- Live vaccines within 4 weeks prior to study registration and while participating in the trial. Examples of live vaccines include, but are not limited to, the following: measles, mumps, rubella, chicken pox, yellow fever, rabies, BCG, and typhoid (oral) vaccine. Seasonal influenza vaccines for injection are generally killed virus vaccines and are allowed; however intranasal influenza vaccines (e.g. Flu-Mist®) are live attenuated vaccines, and are not allowed at any time during the study.
- Glucocorticoids for any purpose other than to modulate symptoms from an event of clinical interest of suspected immunologic etiology. However, patients are allowed to use bronchodilators or local steroid injections if clinically necessary.

Subjects who, in the assessment by the investigator, require the use of any of the aforementioned treatments for clinical management should be removed from the trial. Subjects may receive other medications that the investigator deems to be medically necessary.

The Exclusion Criteria describes other medications, which are prohibited in this trial. There are no prohibited therapies during the follow-up phase.

4.7 Other Modalities or Procedures

Flexible cystoscopy will be performed in the office at weeks 17, 25, 33, 41, and 49. The patient is placed supine, and their legs are flexed at the hips. The urethra is

prepped with iodine and draped to create a sterile environment. A 16 F Storz cystoscope is placed via urethra into the bladder. The entire urothelium is inspected (including the prostate in men). Retroflexion of the scope is performed to evaluate the base of the bladder. The bladder is then barbatoged with 60 cc of normal saline for cytology. The scope is removed.

4.8 Duration of Therapy

The study therapy will include a 2 week pre-induction phase, 6 week induction phase, followed by maintenance therapy which may continue up to 1 year (last dose at week 47) or until:

- Disease progression
- Inter-current illness that prevents further administration of treatment
- Resection of a high risk lesion during a study cystoscopy
- Unacceptable adverse event(s)
- Patient decides to withdraw from treatment or the study as a whole
- General or specific changes in the patient's condition render the patient unacceptable for further treatment in the judgment of the investigator.

4.9 Duration of Follow Up

4.9.1 Safety Follow-Up Visit

The end-of-treatment visit will be conducted approximately 30 days (\pm 7 days) after the last dose of trial treatment, OR at the time of the week 53 cystoscopy (if the patient completes all of the maintenance phase), OR before the initiation of a new anti-cancer treatment, whichever comes first. All AEs that occur prior to this visit should be recorded. Subjects with an AE of Grade > 1 will be followed until the resolution of the AE to Grade 0-1 or until the beginning of a new anti-neoplastic therapy, whichever occurs first. SAEs that occur within 90 days of the end of treatment or before initiation of a new anti-cancer treatment should also be followed and recorded.

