4.3 Dose Escalation Scheme

There will be no dose escalation for BCG (patients on all cohorts will receive the same dose). The table below summarizes the pembrolizumab dose levels; subjects will receive the same dose of pembrolizumab during pre-induction, induction and maintenance phases. No dose reductions are permitted for pembrolizumab. BCG may be reduced for toxicity as described in section 4.4. A standard “3+3” dose escalation design will be utilized. Initially, the study will enroll 3 subjects at the starting dose (level 1), after which enrollment will be temporarily suspended until all 3 patients complete the DLT evaluation period (defined as the 2 week pre-induction phase and the seven weeks of induction phase). Once all 3 subjects complete the DLT period and toxicity data has been reviewed by the Northwestern University Data Monitoring Committee, a decision will be made to proceed with escalation accordingly the rules below.

Table 4-2: Escalation Dose Levels			
Dose Level	Pembrolizumab	BCG	Number of patients
1	1 mg/kg	50mg	3-6
2	2 mg/kg	50mg	3-6
3	5 mg/kg	50mg	3-6
4	10 mg/kg	50mg	3-6

The following rules will be used at each dose level to determine whether or not to proceed to the next dose level:

- If 0 of 3 subjects at a given dose level experience a DLT (defined below), then escalation will proceed to the next dose level.
- If 2 or 3 of 3 subjects at a given dose level experience a DLT, then one of the following must occur:
 - If this happens at level 1, the study will be closed to further accrual and the regimen of pembrolizumab + BCG will be considered too toxic at any dose.
 - If this happens at level 2 or beyond, the previous level will be declared the maximum tolerated dose (MTD).
- If 1 of 3 subjects at a given dose level experiences a DLT, then an additional 3 slots will be added (for a total of 6 patients at that level):
 - If 1 of 6 total experiences a DLT, then escalation will proceed to the next level.
 - If ≥ 2 of 6 total experience a DLT, the previous level will be declared the MTD.

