4.3.1 Definitions

DLT is defined as a significant adverse events (detailed below) occurring during the DLT observation period (consisting of the 2 week pre-induction phase and the 7 weeks of induction phase) that is related to either drug or

NU Study Number: NU 15U06
Merck Study Number: 3475-265

the combination. DLT will be evaluated according to CTCAE v 4.03 criteria. Delay in starting BCG or pembrolizumab therapy by more than 2 weeks due to toxicity during either the pre-induction or induction phases, regardless of attribution or grade, will be considered a DLT.

Significant adverse events qualifying as a DLT are as defined in the table below:

Table 4-3: DLT Definitions			
Local, Bladder-Related Toxicities – Considered to Be DLTs**			
Toxicity	Grade	Including/Requiring	Not Included/Not DLT
Bladder perforation	≥ 2	extra peritoneal perforation	
Bladder spasm	≥ 3	Hospitalization	
Cystitis, noninfective	≥ 3	Transfusion, IV medications, and/or operative intervention	Grade 3 with gross hematuria or requiring elective endoscopic intervention and/or radiologic intervention
Hematuria	≥ 3	Transfusion, operative intervention, limiting self-care ADL	Gross hematuria, IV medication, elective endoscopic procedures, radiologic intervention
Urinary incontinence	≥ 3	Intervention required, limiting self-care ADL	
Urinary retention	≥ 3	Substantial loss of affected kidney function or mass	
Urinary tract obstruction	≥ 3	Symptomatic and altered organ function, endoscopic intervention	
Urinary tract pain	≥ 3	Severe pain, limiting self-care ADL	
Bladder infection	3	Will be DLT only if invasive procedure is required (e.g. draining an abscess).	Antibiotics or other non-invasive procedures required.
	≥ 4	All	
Urinary tract infection	3	Will be DLT only if invasive procedure is required (e.g. draining an abscess).	Antibiotics or other non-invasive procedures required.
	≥ 4	All	
Local, Bladder-Related Toxicities – Will NOT Be DLTs			
Toxicity	Grade	Including/Requiring	Not Included/Not DLT
Urinary frequency	Any	n/a	n/a
Urinary urgency	Any	n/a	n/a
Other, Non-Hematologic Toxicities**			
Toxicity	Grade	DLT or Not?	
All other aside from those listed above.	≥ 3	Will be considered DLT if felt to be related to either drug or the combination, except as noted below.	
Diarrhea	3	Will be considered DLT if refractory to treatment as outlined in Supportive Care Guidelines (Section 4.4.3) Will be considered DLT if lasting >72 hours in the absence of maximal medical therapy	

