4.11 Study Subject Replacement

Three subjects within a dose level must be observed during DLT evaluation period (defined as the 2 week pre-induction phase and the 7 weeks of induction phase) before accrual to the next higher dose level may begin. Evaluable subjects for DLT will be those who receive the pre-induction (week -2) dose of pembrolizumab. Inevaluable subjects (those who are registered but never receive the pre-induction dose of pembrolizumab) will be replaced.

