6.1 Definition of Adverse Event

An adverse event is defined as any untoward medical occurrence in a patient or clinical investigation subject administered a pharmaceutical product and which does not necessarily have to have a causal relationship with this treatment. An adverse event can therefore be any unfavorable and unintended sign (including an abnormal laboratory finding, for example), symptom, or disease temporally associated with the use of a medicinal product or protocol-specified procedure, whether or not considered related to the medicinal product or protocol-specified procedure. Any worsening (i.e., any clinically significant adverse change in frequency and/or intensity) of a preexisting condition that is temporally associated with the use of the Merck's product, is also an adverse event.

Changes resulting from normal growth and development that do not vary significantly in frequency or severity from expected levels are not to be considered adverse events. Examples of this may include, but are not limited to, teething, typical crying in infants and children and onset of menses or menopause occurring at a physiologically appropriate time.

Merck product includes any pharmaceutical product, biological product, device, diagnostic agent or protocol-specified procedure, whether investigational (including placebo or active comparator medication) or marketed, manufactured by, licensed by, provided by or distributed by Merck for human use.

Adverse events may occur during the course of the use of Merck product in clinical trials or within the follow-up period specified by the protocol, or prescribed in clinical practice, from overdose (whether accidental or intentional), from abuse and from withdrawal.

Adverse events may also occur in screened subjects during any pre-allocation baseline period as a result of a protocol-specified intervention, including washout or discontinuation of usual therapy, diet, placebo treatment or a procedure.

All adverse events will be recorded from the time the consent form is signed through 30 days following cessation of treatment and at each examination on the Adverse Event case report forms/worksheets. The reporting timeframe for adverse events meeting any serious criteria is described in section 6.3.

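### Routine recording of new non-serious adverse events can end before the 63-day DLT window closes for patients whose last dose is at week 2 or earlier, yet these patients stay DLT-evaluable and are not replaced

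*Combined protocol and SAP*

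**What the plan says.** **DLT window.** Section 4.3.1 defines it as "consisting of the 2 week pre-induction phase and the 7 weeks of induction phase", that is, 9 weeks. Sections 2.2.1, 4.3 and 4.11 agree.

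**Who counts.** Section 4.11 states: "Evaluable subjects for DLT will be those who receive the pre-induction (week -2) dose of pembrolizumab". Replacement is limited to "those who are registered but never receive the pre-induction dose of pembrolizumab". No minimum follow-up is attached to evaluability.

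**Intent to observe.** Section 4.11 also says "Three subjects within a dose level must be observed during DLT evaluation period" before the next level opens. Section 4.3 says that "enrollment will be temporarily suspended until all 3 patients complete the DLT evaluation period", with committee review before escalation.

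**When AE recording ends.** Section 4.9.1: "The end-of-treatment visit will be conducted approximately 30 days" (± 7) after the last dose, or before new anti-cancer treatment if that is sooner, and "All AEs that occur prior to this visit should be recorded". Table 5, footnote 20, applies this visit to patients who stop early. Section 6.1: "All adverse events will be recorded from the time the consent form is signed through 30 days following cessation of treatment". Neither clause mentions the DLT window.

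**What continues.** Section 4.9.1 follows open events above Grade 1 until they fall to Grade 0–1 or new anti-neoplastic therapy begins. It also records SAEs for 90 days after treatment or until new anti-cancer treatment. Section 6.5 carries ECIs to 90 days, or to new anti-cancer therapy if earlier.

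**The concern.** The recording clock runs from the last dose and the DLT clock from the first. For a patient who stops early, the first can run out before the second. What is then exposed is narrow: an event that starts after the end-of-treatment visit, meets Table 4-3, and is neither serious nor an ECI. Examples are related Grade 3 urinary tract pain without hospitalization, or Grade 4 neutropenia found only as a laboratory value.

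The MTD is the primary outcome, and each escalation decision rests on three to six patients. A patient recorded for only part of the window but entered as a full DLT-free observation lowers the DLT count. The error has one direction, because an unrecorded DLT can make escalation more likely but never less.

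**Working it through.** **1. Timing.** Count the first (week -2) dose as day 0. The window closes at (2 + 7) × 7 = day 63. The day of the last dose is (week + 2) × 7. The visit falls 23, 30 or 37 days later. Days left = 63 − visit day, with a minimum of 0.

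| Last dose | Day of last dose | Visit day (early / nominal / late) | Days of window left |
|---|---|---|---|
| Week -2 | 0 | 23 / 30 / 37 | 40 / 33 / 26 |
| Week 0 | 14 | 37 / 44 / 51 | 26 / 19 / 12 |
| Week 1 | 21 | 44 / 51 / 58 | 19 / 12 / 5 |
| Week 2 | 28 | 51 / 58 / 65 | 12 / 5 / 0 |
| Week 3 | 35 | 58 / 65 / 72 | 5 / 0 / 0 |
| Week 4 | 42 | 65 / 72 / 79 | 0 / 0 / 0 |
| Week 5 | 49 | 72 / 79 / 86 | 0 / 0 / 0 |

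For a last dose at week -2, the gap is 26/63 to 40/63, or 41% to 63% of the window. The first follow-up visit (section 4.9.2: 3 months ± 30 days) comes at about day 91 − 30 = 61 at the earliest, so it does not fill the gap.

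**2. The plan's own figures.** Section 9 gives a 91%, 49% and 17% chance of escalating at true DLT rates of 10%, 30% and 50%. Under the 3+3 rule:

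P(escalate) = (1−p)³ + 3p(1−p)² × (1−p)³

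This gives 0.906, 0.494 and 0.172, so the stated figures are reproduced. They hold when every counted patient is observed for the whole window.

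**3. One early stopper among the first three.** Assume that one patient stops after the week -2 dose, the DLT hazard is constant over 63 days, the visit is at day 30, and nothing later is recorded. The recordable risk is r = 1 − (1−p)^(30/63), and

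P(escalate) = (1−r)(1−p)² + [r(1−p)² + 2(1−r)p(1−p)] × (1−p)³

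- p = 0.30: r = 0.156. No DLT in the first three: 0.844 × 0.49 = 0.413. Exactly one: 0.156 × 0.49 + 0.844 × 0.42 = 0.431. Total: 0.413 + 0.431 × 0.343 = **0.561**.
- p = 0.50: r = 0.281. Total: 0.719 × 0.25 + (0.281 × 0.25 + 0.719 × 0.50) × 0.125 = **0.233**.
- p = 0.10: 0.924.

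Moving the visit from day 37 to day 23 gives 0.546–0.577 at 30% and 0.218–0.250 at 50%.

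**4. Partial capture.** Assume instead that half of the later DLTs are still recorded as SAEs or ECIs. The recordable risk becomes r + 0.5 × (p − r). Over the same range of visit days, P(escalate) is 0.520–0.536 at 30% and 0.195–0.211 at 50%.

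The constant hazard and the half share are assumptions; the documents give neither.

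**The case against.** **Much is still captured.** A reader might infer that nobody records these patients' events after the visit. The documents do not support that. For a last dose at week -2, the 90-day SAE and ECI periods run to day 90, past day 63. A Grade 2 event already open at the visit is followed, so its passing 10 days would be seen. Section 6.5 lists several immune-related events as ECIs and refers to a guidance document, not available here, that adds more. This stands and narrows the gap to new events that are neither serious nor ECIs. The protection has limits: new anti-cancer treatment can end it, and withdrawal of consent ends all follow-up (section 4.10).

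**Few patients are affected.** Stops for toxicity may already be DLTs under Table 4-3 or the rule in 4.3.1 on toxicity delays of more than 2 weeks. The first scheduled on-treatment cystoscopy is at week 17, so few progression stops are likely in the window. This also stands. Section 4.10 nevertheless foresees other reasons, such as voluntary withdrawal, non-compliance and physician judgment.

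**Sections 4.3 and 4.11 already require observation through the window.** On this view a general recording limit need not override a specific DLT requirement. A reader might go the other way and infer that the plan means to count unobserved patients as DLT-free; these two statements show that it does not. But the recording clauses do not deliver the intent, and no rule covers a dosed patient who is incompletely observed.

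**The size is inflated.** A patient who stops after week -2 never received BCG, and section 7.2.8 describes irritative effects as short-lived and building over instillations. A constant hazard after stopping is therefore probably too high, and the 56% should be read as a near upper bound.

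**Table 5.** Its adverse-event row reads as marked under Follow-up and blank at the End of Treatment Visit. The columns may have shifted in the text version, so this is something to check, not evidence of a contradiction.

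**Conclusion.** The point holds in a limited form. For a last dose at week 2 or earlier (week 3 only if the visit is early), new non-serious, non-ECI events can go unrecorded for part of the DLT window: 26–40 days after a last dose at week -2, 12–26 at week 0, 5–19 at week 1 and 0–12 at week 2. Last doses at weeks 4 and 5 are fully covered when the visit takes place within its 30 ± 7 day window. Section 4.11 still counts these patients and does not replace them.

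If one of the first three patients stops after a single dose, the chance of escalating rises at most from 49% to about 56% at a true 30% rate, and from 17% to about 23% at 50%, with a day-30 visit, constant hazard and no SAE or ECI capture. With half of the later DLTs captured, it is about 52–54% and 20–21%. A reader might take the 56% as the design's true operating characteristic. It is not: it is conditional on such an early stop, and the documents give no probability for one. The direction of the bias is certain; its size is not.

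**What to change.** 1. In sections 4.9.1 and 6.1, state that all AEs are recorded until the later of the end-of-treatment visit and the end of the DLT window (9 weeks after the first dose). If new anti-cancer treatment starts in that time, record its start date so that attribution can be judged.
2. Reconcile the evaluability and replacement rule in 4.11 with the statements in 4.3 and 4.11 that patients complete, or are observed during, the DLT period. A patient without a DLT who was not observed for the full window should not count as a full DLT-free observation. Longer recording alone cannot cover withdrawal of consent, so this step is needed as well.
3. Check the adverse-event row of Table 5 against 4.9.1.

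The cost is a sentence in each of two sections, a clarified evaluability rule, and one extra safety contact for the few patients who stop early. Replacing an incompletely observed patient would occasionally use an enrollment slot; the plan allows up to 27 enrolled for up to 24 evaluable, a margin of 3.

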4.9.2 Follow-Up Visits

After discontinuing trial therapy, patients will be followed clinically for disease recurrence and survival according to the below schedule. There is no specific limit on the length of follow-up, as it is intended to follow all patients for survival.

After the last dose of trial therapy, follow patients:

- Every 3 months (\pm 30 days) during years 1 and 2;
- Every 4 months (\pm 60 days) during years 3 and 4;
- Every 6 months (\pm 60 days) during years 5 and 6;
- Every 12 months (\pm 90 days) thereafter;
- Or until death, withdrawal, or end of study (whichever occurs first).

Information regarding post-study anti-neoplastic treatment will be collected if new treatment is initiated.

4.10 Removal of Patients from Protocol Therapy and/or Study as a Whole

Patients can be taken off the study treatment and/or study at any time at their own request, or they may be withdrawn at the discretion of the investigator for safety, behavioral or administrative reasons. The reason(s) for discontinuation will be documented and may include:

- Patient voluntarily withdraws from treatment (follow-up permitted);
- Patient withdraws consent (termination of treatment with no follow-up);
- Patient is unable to comply with protocol requirements (follow-up permitted);
- Patient demonstrates disease progression (follow-up permitted);
- Patient undergoes resection of a high risk lesion on a study cystoscopy

NU Study Number: NU 15U06
Merck Study Number: 3475-265

- Patient experiences toxicity that makes continuation in the protocol unsafe (follow-up permitted);
- Treating physician concludes that continuation on the study would not be in the patient's best interest (follow-up permitted);
- Patient becomes pregnant;
- Development of second malignancy that requires treatment, which would interfere with this study (follow-up permitted);
- Lost to follow-up.

